1) Background/Significance

Stigma remains a pernicious impediment to health for gay, bisexual, and other men who have sex with men (MSM), discouraging their disclosure of health-related conditions and sexual activities; deterring their access to HIV prevention tools; and impinging on their psychological wellbeing. During healthcare encounters in particular, stigma confronts MSM with a vexing dilemma: disclose sexual activity to access MSM-specific care or conceal it to avoid discrimination but remain distanced from the HIV interventions and services they desperately need. Engaging at-risk MSM requires that healthcare workers (HCWs) communicate in ways that mitigate rather than exacerbate pervasive stigma toward their sexual behavior, and specifically toward anal sex, the most proximate risk factor for HIV infection among MSM. HCWs report a lack of knowledge and skill assessing MSM's sexual behavior and, unsurprisingly, discomfort conducting sexual histories, thereby missing opportunities to triage for HIV/STI interventions. Multicomponent, intersectional strategies can train HCWs to prevent enacting stigma, but are also needed to help HCWs proactively inoculate MSM against internalized and anticipated stigma that otherwise would continue to deter care. To date, however, there are no tested, evidencebased programs to mitigate stigma toward anal sexuality. Consequently, MSM remain deterred from discussing the very sexual activity that places them at greatest risk of HIV acquisition and transmission. Through this study, we intend to develop, pilot, and evaluate a new behavioral HIV intervention for HCWs to mitigate anal sex stigma, in order to improve both the quality of care and HIV-related outcomes among MSM.

2) Study Design

We describe study design for Aim 1 and Aim 2, because we are awaiting approval from an NIMH program officer for Aim 3 study design changes to the funded protocol. An amendment will be submitted prior to conducting any activities for Aim 3.

Aim 1: Explore drivers that perpetuate and techniques and mechanisms that mitigate anal sex stigma during healthcare encounters by interviewing a diverse sample of HCWs (N = 20) and MSM (N = 20) in the US.

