Aim 2: Develop an intersectional stigma-mitigation intervention with mHealth, workshop and coaching components, in collaboration with an 8-person Advisory Board of MSM/healthcare consumers and HCWs and informed by Aim 1, to improve HCW competence to discuss anal health and sexuality and thereby promote HIV prevention.

Aim 3: Pilot the intervention in a pre-post, sequential explanatory mixed method design among 120 HCWs who do not specialize in MSM care, working in two regions where HIV incidence among MSM remains high. Longitudinal surveys and select follow-up interviews will evaluate: (a) implementation outcomes (i.e., acceptability, feasibility, and appropriateness) and (b) preliminary impact on mechanisms of action (e.g., knowledge, skills, intention, resources) as well as HIV/STI screening activities (e.g., initiating assessment of sexual behavior).

In Aim 1, we conducted a mixed-methods sequential explanatory design. This involved an online survey to screen and purposively sample 20 cisgender MSM and 20 HCWs, followed by a onetime, hourlong in-depth interview with these same participants. To be eligible, MSM needed to report: being aged 18 or older, identifying as male, residing in the US, being able to read and communicate in English, and having had anal intercourse with a man in the past year or intend to in the next year. HCWs needed to report: being aged 18 or older, being able to read and communicate in English, bearing a role responsibility for HIV-related screening and referral (e.g., as a peer/outreach worker, test counselor, case manager, social worker, medical assistant, nurse, physician assistant, physician). The primary outcome of Aim 1 is to identify qualitatively a set of techniques and mechanisms that could mitigate anal sex stigma during clinical encounters between HCWs and MSM and that would be acceptable, feasible and appropriate for both HCWs and MSM populations. We conducted rapid qualitative analysis, using debriefing forms after each interview and then templates to extract constructs from our qualitative inquiry guide. These were then added to a spreadsheet that also contained survey responses, and then a matrix analysis was conducted to establish themes for barriers, facilitators, techniques and mechanisms of action.

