For both Aim 1 and Aim 2, participants needed to be 18 years or older for both Aim 1 and Aim 2. We also purposefully sampled for participants living with HIV to ensure that we collected data on the lived experience of people living with HIV for the intervention. The sample sizes for Aim 1 and Aim 2 were established based on an estimate of saturation of qualitative themes, for Aim 1, and based on the likelihood of sustained engagement and group cohesion during meetings, for Aim 2.

For Aim 3, a total of 120 HCWs will be recruited in two regions. To yield n = 60 intervention participants per region, we will aim for n ~90 consented, estimating a conservative 70% retention rate based on the AETC and similar procedures in Ohio and China. Prior to implementation of the intervention, we plan to interview approximately 5 clinic staff within each region, to inform tailoring the intervention to their local context. A subset of 15 HCWs in each region will be purposively sampled for post-intervention interviews based on initial observations, survey responses and reactions during intervention, racial/ethnic diversity, and diversity of professional role.

- b) Inclusion criteria are the same as those stated in (2) Study Design.
- c) Minors were not included because a separate, age-specific study in adolescent cisgender males who have sex with males is warranted and preferable. Non-English speaking people were excluded due to limitations in the study team's ability to conduct surveys, interviews and Advisory Board meetings in languages other than English. There were no exclusion criteria.

Please note that the Inclusion Enrollment Reports in the original K23 proposal (a resubmission) mistakenly did not include women, even though the initial proposal did include women. The correct gender, racial and ethnic breakdown is below.

Women are overrepresented in the field of healthcare but will comprise ~40% of HCW interviews. The remaining ~60% of HCWs will be among men and other gender identities, some of whom identify as MSM themselves. We are targeting enrollment of more men and other genderidentities than women in order to include MSM HCWs, who will likely have valuable insights to share in their dual role as both a sexual minority male and a HCW.

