their interest in participation. This same process has been used to approach and recruit additional Advisory Board members who did not participate in Aim 1, with a slightly adapted message to introduce the study.

For previous participants, no advertising or publicity is necessary; we will simply follow up with them about their interest in participating in Aim 2's Advisory Board. For the additional Advisory Board members who did not participate in Aim 1, we do not plan advertising or publicity, except to consult within professional networks of healthcare providers and colleagues who collaborate with scholars and providers of nonbinary and transgender participants and patients, to develop a list of potential Advisory Board members.

For both Aim 1 and Aim 2: Prior to interviews and Advisory Board meetings as well as during both of these procedures, participants were reminded that their participation is voluntary and that they could decline to answer any question posed during the course of the study and could decline to participate any further at any point during the study.

For Aim 3, recruitment will be done in collaboration with two AETC regional collaborators. These AETC collaborators report sufficient community interest in this topic to feasibly recruit 120 HCWs and will introduce study staff to local healthcare leaders and community-based organizations to cultivate partnerships. Recruitment will occur through regional outreach, using the existing infrastructure and relationships of the AETC. Potential participants will then receive an email invitation, citing these partnerships. A link to an online Information Statement will describe study procedures and follow with demographic and psychosocial questions as part of the baseline assessment.

5) Informed Consent

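### Does the plan count on recruiting only 120 healthcare workers for Aim 3 when its own retention allowance calls for about 180 consents?

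*Protocol*

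**What the plan says.** The number 120 appears three times for Aim 3.

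- Section 2 (Study Design) describes the pilot as a pre-post "design among 120 HCWs who do not specialize in MSM care".
- Section 3 (Study Population) opens its Aim 3 paragraph with "For Aim 3, a total of 120 HCWs will be recruited in two regions".
- Section 4 (Participant Recruitment) reports the view of the two regional training-center partners: "These AETC collaborators report sufficient community interest in this topic to feasibly recruit 120 HCWs".

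The consent target appears once, in section 3, directly after the 120: "To yield n = 60 intervention participants per region, we will aim for n ~90 consented". The allowance behind it follows in the same sentence: "estimating a conservative 70% retention rate". The protocol does not print a two-region consent total.

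Section 2 also says that Aim 3 design changes await the funder's approval: "An amendment will be submitted prior to conducting any activities for Aim 3".

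**The concern.** In section 3, *recruited* goes with 120 while *consented* goes with about 90 per region, which is about 180 over two regions. Two neighboring sentences thus seem to give different sizes for the same intake.

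Section 4 makes this look worse. It describes recruitment as regional outreach, after which "Potential participants will then receive an email invitation, citing these partnerships"; the online Information Statement and baseline questions come next. Recruiting in that sense precedes consent, so one would expect the feasibility sentence to name at least the consent target. It names 120, and no other sentence says that interest suffices for about 180.

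If the partners had vouched for only 120 consents, the pilot could lose 30% of them and end well under its intended size. Its descriptive implementation outcomes and its paired comparisons would then rest on fewer people than planned.

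**Working it through.** **Inputs.** All come from section 3, except that the feasibility figure of 120 is from section 4: 60 intervention participants per region, two regions, about 90 consented per region, 70% retention.

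**The plan's own figures**

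- Total: 2 × 60 = 120. This reproduces the 120 exactly, as the number of intervention participants.
- Consents needed per region: 60 / 0.70 = 85.7, so 86. The plan writes about 90. That is not the exact quotient but an upward rounding, on the safe side.
- Consents in total: 2 × 90 = 180 as planned, against a minimum of 2 × 86 = 172.

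**Is the consent target enough?**

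- Per region: 90 × 0.70 = 63, against 60.
- In total: 180 × 0.70 = 126, against 120.

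So 120 is the target and 126 is the expected yield; the plan carries a small margin. If each consented worker is retained independently with probability 0.70 (an assumption made here), the chance of at least 60 in a region is about 0.79 with 90 consents and about 0.57 with 86. The rounding up is therefore useful.

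**What if 120 meant consents?**

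- Yield: 120 × 0.70 = 84 in total, or 42 per region, which is 36 short of 120.
- Share of the consent target covered: 120/180 = 67%, or 120/172 = 70% of the minimum.
- Gap: 180 − 120 = 60 consents, or 172 − 120 = 52 at the minimum.

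**Which reading does the text support?**

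| Place | Number | Fits 120 = intervention participants? | Fits 120 = consents? |
|---|---|---|---|
| Section 2, pilot sample | 120 | Yes | No, the pilot would then run among about 84 |
| Section 3, Aim 3 total | 120 | Yes, 2 × 60 | No, the next sentence sets about 90 consents per region |
| Section 4, feasibility | 120 | Yes, as the study's headline size | Possible in isolation |

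The first reading makes all three places agree. The second conflicts with section 3 and with the pilot size in section 2.

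**The case for a change.** The strongest case for a correction has three parts.

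First, the protocol never defines *recruit* as bringing someone into the intervention, and section 4 sets out recruitment as steps that come before consent. Second, about 180 people would consent and be asked baseline questions, yet the only Aim 3 total in print is 120. For Aim 1, section 3 gives both levels: 250 per group to enroll and 20 per group to interview. Third, the partners' statement is the only evidence of recruitment feasibility for Aim 3, and doubling 90 does not show which number they had in mind.

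Part of this stands. The verb is used loosely, and section 4 does not say which count its 120 refers to.

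The rest does not carry far. Read strictly, the order of steps in section 4 would make 120 the number approached before invitation, and that cannot be squared with about 180 consents on any view. The sentence is better read as naming the study's headline sample. It also claims sufficient interest for that sample; it does not say that interest ends at 120, and nothing in the protocol makes 120 a ceiling on consents. What the partners were asked is not in the document, so a feasibility gap can be supposed but not shown. The missing total is one multiplication away from a figure that is printed.

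**Conclusion.** The concern does not call for a change. It is a clerical looseness of wording, and the sentence next to it resolves it. The consent target allows for the stated loss, with an expected 126 intervention participants against 120. Section 7 (Data Analysis) plans descriptive statistics and paired t-tests for Aim 3, and neither depends on how the 120 is labeled. The deficit of 52 to 60 consents, with a yield of 84, arises only if 120 means consents, which section 3 excludes as the plan.

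This rests on two assumptions: that the 70% covers the step from consent to intervention participation, as the sentence in section 3 implies, and that the 120 in section 4 is the same headline number as in sections 2 and 3. If the second were wrong, the doubt would concern how much the partners' assurance covers. The number of consents the team must seek would stay the same. The Aim 3 amendment is a natural place to tidy the wording should the authors wish, but the conduct and analysis of the pilot do not depend on it.

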In Aim 1, we conducted interviews by telephone or video through Zoom Pro. In Aim 2, Advisory Board participants may choose to keep their cameras off and/or to change their screen name, if they would like to remain more anonymous to their fellow Advisory Board members. In Aim 3, telephone or video through Zoom Pro will also be used. Written consent is the only link between the subject's identity and the research data, so we have requested a waiver of documentation of consent in order to remove the risk of a breach of confidentiality for research participants during their participation in all aims of the study.

Aim 1 participants were compensated for their time completing hourlong interviews with a \$50. Aim 2 Advisory Board members are being compensated \$100 for participation in each of six to eight ~90-minute meetings over the course of nine months, of which two have already occurred. Aim 3 participant compensation will vary depending on their participation in each assessment, ranging between \$90 and \$190 (\$50 for each in-depth interview, with a maximum participation of two interviews per participant, and \$30 for each survey, with a maximum participation of three surveys).

6) Risk/Benefit

The risks are the same in Aim 1, Aim 2 and Aim 3:

- a) The main risk of study participation is loss of confidentiality and potential consequences thereof. An unintended person (e.g., family members, employers) could find out about a participant's sexual identity, sexual behavior, HIV status as well as their stigmatized or stigmatizing behavior. Unintentional disclosure of sexual minority status may place participants at risks for social harm such as exclusion from family, job loss, harassment, and discrimination.
- b) Additional risk for participants includes distress when discussing issues related to stigma during healthcare encounters. The MSM population and other healthcare consumer populations who practice anal sex engage in behavior that is socially stigmatized and HCWs may themselves experience embarrassment with regard to the sexual subject matter, whether or not they engage in similar behavior. HCWs may also experience distress at the recognition, during assessments, that their own beliefs and actions could be perceived as perpetuating stigma toward their

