The primary outcome of Aim 1 is qualitative, to identify a set of techniques and mechanisms that could mitigate anal sex stigma during clinical encounters between HCWs and MSM and that would be acceptable, feasible and appropriate for both HCWs and MSM populations. We conducted rapid qualitative analysis, using debriefing forms after each interview and then templates to extract constructs from our qualitative inquiry guide. These were then added to a spreadsheet that also contained survey responses, and then a matrix analysis was conducted to establish themes for barriers, facilitators, techniques and mechanisms of action.

The primary outcome of Aim 2 is to elicit feedback from the Advisory Board and to develop the intervention. Data analysis involves taking notes based on each Advisory Board meeting and then consulting within the research team to revise plans for intervention development based on the Advisory Board's recommendations.

The primary outcomes of Aim 3 are both qualitative and quantitative, to assess implementation outcomes as well as preliminary effects of the intervention among healthcare workers. As in Aim 1, for Aim 3 we will conduct rapid qualitative analysis, using debriefing forms after each interview and then templates to extract constructs from our qualitative inquiry guide. These will then be added to a spreadsheet that also contains survey responses, and then a matrix analysis will conducted to establish themes. For quantitative data, we will assess implementation outcomes using descriptive statistics and assess changes in mechanisms of action, behavior and quality of care using paired t-tests.

8) Data quality control and database management.

For Aim 1 and Aim 2, quantitative data have been collected via online surveys, downloaded and imported into SPSS and then stored on SharePoint in password-protected files. Audio files are downloaded and stored on OneDrive for Business along with transcripts, all in password protected files. The Principal Investigator conducts data quality control and checking and editing quantitative data. In Aim 2, data has been been stored in REDCap and managed on a daily basis by the study's research coordinator, [name], with oversight by the PI. All data are stored only on password protected, HIPAA-secure websites. Aim 3 will continue the same data collection and storage procedures as Aim 2.

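### Aim 3 collects up to three surveys per healthcare worker but tests change only with paired t-tests, which drop anyone missing either survey of a pair (minor)

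*Protocol*

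**What the plan says.** Section 2 (Study Design) describes Aim 3 as a single-group pre-post pilot in 120 healthcare workers: "Longitudinal surveys and select follow-up interviews will evaluate" implementation outcomes and "preliminary impact on mechanisms of action", along with screening activities. Section 5 (Informed Consent, compensation) pays 30 dollars "for each survey, with a maximum participation of three surveys". It adds that "Aim 3 participant compensation will vary depending on their participation in each assessment", so survey participation is expected to differ between workers.

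Section 7 (Data Analysis) splits the quantitative work in two. For the first part, "we will assess implementation outcomes using descriptive statistics". For the second, the plan is to "assess changes in mechanisms of action, behavior and quality of care using paired t-tests". No other method for change is named, and the text does not say which two of the three surveys form a pair.

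Section 3 (Study Population) gives the only retention figure: "To yield n = 60 intervention participants per region, we will aim for n ~90 consented, estimating a conservative 70% retention rate". Section 2 also states of the Aim 3 design: "An amendment will be submitted prior to conducting any activities for Aim 3".

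**The concern.** A paired t-test uses two surveys and only the people who have both. With three surveys, a worker who answers the first two and misses the third contributes to the baseline-to-first-follow-up test, but adds nothing to the test of change at the last survey. Yet that worker's first two surveys carry information about the missing third.

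Two things are at stake for the last-survey change. One is a modest loss of precision. The other is bias when loss is related to early change, or to a baseline level that is itself correlated with change. Workers who found the workshop useful may be likelier to keep answering, and the completers' mean change would then overstate the effect. Preliminary impact is one of the two things Aim 3 sets out to evaluate, so the last-survey estimate is one of the pilot's main products.

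**Working it through.** **The plan's own figures.** Three surveys at 30 dollars give 3 × 30 = 90, and two interviews at 50 dollars bring this to 90 + 100 = 190. This is the stated payment range and confirms a maximum of three surveys. For recruitment, 60 / 0.70 = 85.7, so 86, which the protocol rounds up to about 90 (90 × 0.70 = 63). That 70% runs from consent to intervention participation. It is not a return rate for the third survey and is not used as one here.

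**Assumptions (not in the protocol).** n = 120; surveys T0, T1, T2 with SD 1; true change 0.30 SD at T1 and T2; loss only at T2, of 10%, 20% or 30%. Correlations T0–T1 / T0–T2 / T1–T2 are 0.5 / 0.5 / 0.5 (set A) or 0.4 / 0.3 / 0.7 (set B).

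**Complete data.** The paired estimate and the unstructured three-survey model give the same change, so they differ only where surveys are missed.

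**Random loss.** Let p be the share returning T2, V = 2(1 − ρ02) the variance of the change, and s² the variance of T2 given T0 and T1.
- Paired SE = √(V / (120p)).
- Model SE = √((V + s²(1/p − 1)) / 120).
- Set A: V = 1, s² = 0.667. At 10/20/30% loss, paired 0.096/0.102/0.109 and model 0.095/0.099/0.104; the paired SE is 2/4/5% larger.
- Set B: V = 1.4, s² = 0.510. Paired 0.114/0.121/0.129 and model 0.110/0.113/0.116; the paired SE is 3/7/11% larger.

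At 30% loss, 0.70 × 120 = 84 pairs remain. Neither method is biased.

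**Selective loss.** Let X, scaled to SD 1, drive return of T2 on the logistic scale. Then paired bias = Cov(T2 − T0, X) × δ, where δ is the mean of X among those who return T2. For log-odds 0.5 per SD, numerical integration gives δ = 0.049/0.096/0.143 at 10/20/30% loss; for log-odds 1.0, δ = 0.091/0.173/0.253. The covariances are:
- X = early change (T1 − T0): A 0.5; B (0.7 − 0.3 − 0.4 + 1)/√1.2 = 0.913.
- X = baseline: A 0.5 − 1 = −0.5; B 0.3 − 1 = −0.7.
- X = T1 level: A 0.5 − 0.5 = 0; B 0.7 − 0.4 = 0.3.
- X = last change (T2 − T0): A 1; B √1.4 = 1.183.

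Expected paired estimate (truth 0.30) at 10/20/30% loss:

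| Return of T2 depends on | Log-odds per SD | Set A | Set B |
|---|---|---|---|
| Early change | 0.5 | 0.324/0.348/0.371 | 0.345/0.388/0.430 |
| Early change | 1.0 | 0.345/0.387/0.426 | 0.383/0.458/0.531 |
| Baseline level | 0.5 | 0.276/0.252/0.229 | 0.266/0.233/0.200 |
| T1 level | 0.5 | 0.300 throughout | 0.315/0.329/0.343 |
| Last change (partly unseen) | 0.5 | 0.349/0.396/0.443 | 0.358/0.414/0.469 |

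Simulation (10,000 replicates) agrees with every entry within 0.003. In the first four rows the unstructured model gives 0.298 to 0.303. In the last row it gives 0.334/0.365/0.397 (A) and 0.321/0.343/0.363 (B), so bias remains when data are not missing at random.

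With loss driven by early change at log-odds 0.5, a true zero change is rejected by the paired test in 6/8/10% (A) and 7/12/17% (B) of trials, against a nominal 5%.

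A separate simulation with n = 60 or 120, common correlations of 0.3 to 0.7, 15% or 30% loss and log-odds 1 gave paired bias of +0.05 to +0.15 SD for loss by early change and −0.04 to −0.18 SD for loss by baseline. Model bias stayed within 0.01. When change was unrelated to baseline, loss by baseline caused no bias.

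**The case against.** The strongest reply is that this is a missing-data question, which belongs in a statistical analysis plan that is not at hand. The protocol states no complete-case rule, and a paired t-test could follow imputation. This stands in part: a missing imputation rule would not be a finding. But the protocol does fix the test, and that test as ordinarily applied uses two surveys and complete pairs in a design that allows three.

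Second, nothing in the protocol shows that later surveys will be missed. The 90-dollar payment floor equals three completed surveys, and no loss after the intervention is stated. Nor does the protocol say that every change outcome is measured three times. Both points stand. They make the size conditional and confine the remedy to outcomes measured more than twice.

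Third, the model is not a cure-all. Section 3 gives coaching after the workshop only to workers at a specific target site. If coaching affects both retention and outcome, a model with only time and region shares the paired test's bias. With half coached, return log-odds 1.0 higher in the coached, a 0.3 SD coaching difference at the last survey and 30% loss (all assumed), both gave 0.32 against a true 0.30. This stands as a reason to add coaching to the model, which brought the estimate back to 0.30.

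**Conclusion.** The point holds and is minor. The change estimate at the last survey is exposed to a small loss of precision and to a bias whose direction depends on who is lost. Baseline to first follow-up is unaffected under the assumed pattern of loss.

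There is no bias if loss is random, if it depends on a baseline level unrelated to change, or if it depends only on the first follow-up level and that level has equal covariance with baseline and last survey. All sizes above rest on assumed loss, correlations and effect. The study is a pilot of preliminary effects with no power claim, and neither method makes up for the lack of a control group.

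**What to change.** In section 7, for change outcomes measured at more than two surveys, replace the paired t-tests with: *a likelihood-based linear mixed model for repeated measures with categorical time, region and an unstructured covariance, fitted to all available surveys from intervention participants, reporting contrasts of each follow-up with baseline and 95% confidence intervals; for binary items, multiple imputation using all survey waves.* Consider adding coaching status, with an effect that may differ by survey.

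Keep paired t-tests as a completer sensitivity analysis and as the main test for outcomes measured only twice. State that the model removes bias only if data are missing at random and does not replace a control group.

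The detail matters. A random-intercept (compound-symmetry) model in set B at 30% loss still gave 0.352 and 0.390 for early-change log-odds of 0.5 and 1.0. For a binary item with a true change of 0.120, and 30% loss depending on the first follow-up answer (log-odds 1), an independence GEE gave 0.144 (A) and 0.156 (B). An all-wave estimate, the limit of all-wave imputation, gave 0.121 and 0.120.

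The cost is one sentence and slightly more analysis work. An unstructured covariance for three surveys has 6 parameters, which 120 participants can support. No new data or participants are needed, and the change can go into the amendment already promised before Aim 3 starts.
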